5.4.2.4 Overall Survival

OS is defined as the time from initiation of study invention until death due to any cause. Participants who are not reported as having died at the time of analysis will be censored at the most recent contact date they were known to be alive. See Section 5.6.2 for handling of missing or partial death dates.

OS will be estimated using Kaplan-Meier techniques, and the median survival time and 95% CIs will be estimated within each cohort. If median survival is not reached, survival times and 95% CIs will be reported at deciles that are estimable given the observed events. In addition, the 12-month OS rate will be estimated within each cohort and 95% CIs will be estimated using the Clopper-Pearson method.

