Response rates for ORR, DCR, and OS will be estimated within each immunotherapy combination cohort and 95% CIs will be estimated using the Clopper-Pearson method. rPFS and OS will be estimated using Kaplan-Meier techniques, and the median survival time and 95% CIs will be estimated within each immunotherapy combination cohort. If median survival is not reached, survival times and 95% CIs will be reported at deciles that are estimable given the observed events.

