3.4 Analysis Timing

The primary analyses described in the main body of this document will be performed for each immunotherapy combination cohort separately after all participants for a specific cohort have at least 6 months of follow-up from the date of first dose or have discontinued the study. Each cohort will be assessed independently of the other cohorts, and the data from each cohort will be analyzed separately. Study conduct of one or more cohorts may be ongoing at the time of final analysis for a given cohort.

Any cohort-specific modifications to the statistical methods, including any additional cohort-specific endpoints, will be captured as an appendix in this SAP.

Analysis of safety and efficacy endpoints will be performed prior to the time of primary analysis. These analyses will help inform adaptations of the trial, such as expanding, modifying, or terminating a cohort. More information about these interim analyses is presented in Section 5.7. These results may be presented and/or published prior to the primary analysis.

A cohort will formally end once all participants have been followed for survival status for a maximum of 2.5 years or until death, withdrawal of consent, or loss to follow-up. The Sponsor may choose to discontinue survival follow-up of a cohort at any time. A survival analysis of long-term follow-up may be performed after the primary analysis has been completed.

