5.4 Efficacy Analysis

The analyses for clinical activity will be performed on the evaluable population, consisting of all participants in a cohort who received at least 1 dose of any component of the combination study intervention. Some efficacy endpoints may be analyzed on a subset of the evaluable population, as summarized in Table 3.

This study is not intended or powered for hypothesis testing or comparison between cohorts. Due to the exploratory nature of this study, no control of type I error will be applied for any of the endpoints.

Table 3: Populations for Efficacy Analysis

Endpoint	Analysis Population
CRR	Evaluable population
CTC response (component of CRR)	Participants with a baseline CTC value ≥ 5 cells/7.5 mL of blood
PSA response (component of CRR)	Participants with a PSA value at baseline
ORR (component of CRR)	Participants with measurable disease at baseline per PCWG3-modified RECIST v1.1
DCR	Evaluable population
rPFS	Evaluable population
OS	Evaluable population
Change in CTC from baseline	Participants with a CTC value at baseline
CTC0	Participants with a baseline CTC value ≥ 1 cell/7.5 mL of blood
Percent change in PSA from baseline	Participants with a PSA value at baseline
Time to PSA progression	Participants with a PSA value at baseline
DOR	Participants with measurable disease at baseline per PCWG3-modified RECIST v1.1 and a best overall response of CR or PR

CR = complete response; CRR = composite response rate; CTC = circulating tumor cells; CTC0 = a measure of zero CTC; DCR = disease control rate; DOR = duration of response; ORR = objective response rate; OS = overall survival; PCWG3 = Prostate Cancer Clinical Trials Working Group 3; PR = partial response; PSA = prostate-specific antigen; RECIST = Response Evaluation Criteria in Solid Tumors; rPFS = radiographic progression-free survival

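### SAP 5.4.2.4 gives the 12-month OS rate a Clopper-Pearson interval although status at month 12 may be censored, and does not say that the rate is the Kaplan-Meier value

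*SAP*

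**What the plan says.** SAP 5.4.2.4 defines OS from the start of study intervention to death. Participants not reported dead "will be censored at the most recent contact date they were known to be alive". It continues: "OS will be estimated using Kaplan-Meier techniques, and the median survival time and 95% CIs will be estimated within each cohort". It then adds a separate sentence, under which "the 12-month OS rate will be estimated within each cohort and 95% CIs will be estimated using the Clopper-Pearson method". That sentence names an interval but no estimator.

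SAP 3.4 sets the primary analysis of a cohort at the point when all its participants "have at least 6 months of follow-up from the date of first dose or have discontinued the study". It lets the sponsor end survival follow-up at any time. Of later data it says only: "A survival analysis of long-term follow-up may be performed after the primary analysis has been completed".

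Nothing else settles the estimator:

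- Protocol 9.3.1.2 points both ways. One sentence opens "Response rates for ORR, DCR, and OS will be estimated within each immunotherapy combination cohort", with Clopper-Pearson intervals. The next says "rPFS and OS will be estimated using Kaplan-Meier techniques".
- SAP 5.4 states: "Some efficacy endpoints may be analyzed on a subset of the evaluable population, as summarized in Table 3". Table 3 places OS in the full evaluable population and has no separate line for the 12-month rate.
- SAP 5.6 covers adverse event dates and death dates only, and SAP 6 lists no change to the OS analysis.
- SAP 5.4.2.2 does give a counting rule for short follow-up in DCR. The 12-month OS rate has none.

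**The concern.** A Clopper-Pearson interval describes x successes out of n when the outcome of all n is known. A participant last seen alive at month 8 is neither a success nor a failure at month 12. To obtain a count, the analyst must treat such participants as alive, drop them or treat them as not alive, and the SAP does not say which. Kaplan-Meier needs no such choice, but the sentence on the 12-month rate does not invoke it, and the interval it names is the one used for CRR and DCR.

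The 12-month OS rate is a named secondary endpoint, and SAP 3.3 says that the study's estimates are meant to help design later studies. The same data could yield materially different published rates, depending on how a programmer reads one sentence.

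**Working it through.** **Inputs.** From the documents: n = 15 or 30, 95% two-sided intervals, earliest cut 6 months after the last first dose, censoring at last contact. The documents give no accrual time and no expected OS, so both are assumed below.

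**1. The plan's own figures.** Clopper-Pearson limits are: lower = 2.5% quantile of Beta(x, n-x+1); upper = 97.5% quantile of Beta(x+1, n-x). For 5/15 this gives 11.8% to 61.6%, and for 6/15 it gives 16.3% to 67.7%. Both match SAP Table 2, as do its other ten intervals. The method is sound where status is known for everyone.

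**2. One constructed data set, n = 15.** Deaths at months 2, 4, 7, 9 and 11; five participants censored alive at months 6.5, 7.5, 8.5, 9.5 and 10.5; five seen alive past month 12.

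- Unknowns as alive: 10/15 = 67% (38% to 88%).
- Unknowns excluded: 5/10 = 50% (19% to 81%).
- Unknowns as not alive: 5/15 = 33% (12% to 62%).
- Kaplan-Meier: numbers at risk at the five deaths are 15, 14, 12, 9 and 6. S(12) = 13/15 x 11/12 x 8/9 x 5/6 = 58.8%.

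The Greenwood sum is 1/(15x14) + 1/(14x13) + 1/(12x11) + 1/(9x8) + 1/(6x5) = 0.0651. On the log(-log) scale the standard error is sqrt(0.0651)/|ln 0.588| = 0.481. The exponent is exp(1.96 x 0.481) = 2.57. The limits are 0.588^2.57 = 25.6% and 0.588^(1/2.57) = 81.3%. Clopper-Pearson limits placed around 15 x 0.588 would be 31% to 83%.

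**3. Simulation.** Assumptions: exponential OS with median 9, 12, 18 or 24 months (12-month OS 40%, 50%, 63% or 71%), uniform accrual, the earliest permitted cut, and living participants censored at the cut. With 12-month accrual and n = 15, 29% to 44% are censored before month 12. Ranges run over the four medians; bias is in percentage points.

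| Reading, 12-month accrual | Bias, n = 15 | Coverage, n = 15 | Coverage, n = 30 |
|---|---|---|---|
| Unknowns as alive | +4 to +7 | 94-98% | 91-96% |
| Unknowns excluded | -15 to -17 | 89-91% | 78-81% |
| Unknowns as not alive | -22 to -40 | see below | see below |
| Kaplan-Meier, where the curve reaches month 12 | within 1 | about 94-96% with Clopper-Pearson limits | same |

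For unknowns counted as not alive, a separate run with a true rate of 60% gave coverage of 42% at n = 15 and 6% at n = 30. Log-log limits around Kaplan-Meier covered 95% to 97%.

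**4. Sensitivity, n = 15.**

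- Slower accrual at the earliest cut: with 24 months, bias is +2.5 to +4.3 (alive) and -6.4 to -7.2 (excluded).
- Later cut, 12-month accrual: at last first dose plus 9 months, bias is +1.2 to +2.0 and -7.4 to -8.2. At plus 12 months it is about 0 and about -1.
- Last contact up to 3 months before the cut (survival calls are 3-monthly), with later deaths unseen: at the earliest cut, Clopper-Pearson limits around Kaplan-Meier cover about 91% to 92%, and about 90% at a 9-month median. At plus 12 months, 8% to 14% are still censored before month 12.
- Fast accrual of 6 months at the earliest cut: the curve stops short of month 12 in 94% to 99% of replicates.

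**5. What is unaffected.** The two-stage rule (15 then 30 participants; at least 2, then at least 6 responses) recomputes to a type I error of 0.068, power of 0.774 and early-stop probability of 0.549. These match the stated 0.07, 77% and 55%. OS does not enter the rule.

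**The case against.** The strongest reply is that Kaplan-Meier is plainly meant. The paragraph defines OS with a censoring rule and names Kaplan-Meier before it turns to the 12-month rate, and nothing in it drops or recodes censored participants. Table 3 keeps OS in the whole evaluable population, which fits poorly with excluding unknowns. The SAP also supersedes the protocol (SAP 2; Protocol 9.3), so the mixed wording in Protocol 9.3.1.2 does not govern. Most of this stands. It reduces the size of the problem, but leaves an interval that does not fit a censored estimate and a sentence that can be programmed literally.

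Second, the large biases depend on assumed accrual and survival and on the earliest cut. That also stands: SAP 3.4 sets a minimum of 6 months and does not commit to analysing then. But the later survival analysis is optional, so the plan does not guarantee that the problem goes away.

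Third, Kaplan-Meier is not free of bias in every case. If deaths are known up to the cut while the living are censored at an earlier contact, it runs about 3 points low at the earliest cut. That is still better than excluding unknowns or counting them as not alive; showing the number censored lets a reader judge it.

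A reader might infer that the reported OS rate will be wrong by 15 points or more, or that expansion decisions are compromised. The documents support neither. The first needs a crude-proportion reading that the paragraph does not favour, and SAP 5.7.1 rests expansion on CRR and safety.

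**Conclusion.** The concern holds in a limited form: the stated interval does not fit data that may be censored before month 12, and the estimator is left to inference. On the natural Kaplan-Meier reading this is a mismatch with little effect, except that coverage slips to about 90% to 92% when last contact lags the cut. On a literal reading the rate is biased, and the direction and size turn on an unstated choice: from about +7 to about -40 points across the three ways of counting unknowns. Those figures rest on n = 15, an assumed 12-month accrual, exponential survival with medians of 9 to 24 months, and the earliest permitted cut. The bias shrinks as accrual slows or the cut moves later.

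The endpoint is secondary and descriptive, the study is not powered for hypothesis testing, and the design's error rates are untouched. The point is minor to moderate, and worth correcting because the correction is so cheap.

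**What to change.** In SAP 5.4.2.4, state that:

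- the 12-month OS rate is the Kaplan-Meier estimate at month 12 in the evaluable population, with a Greenwood-based log-log 95% interval;
- the number at risk at month 12 and the number censored before it are shown beside the estimate;
- the rate is reported as not estimable at any cut where the curve does not reach month 12;
- if nobody is censored before month 12, Clopper-Pearson may be used for this rate;
- at an estimate of 0% or 100%, where log-log limits are undefined, an exact binomial interval on the number with known month-12 status is given and labelled as such.

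Keep Clopper-Pearson for CRR, its components and DCR. There is no need to bar reporting until everyone has 12 months of potential follow-up: waiting does not by itself name the estimator, and some participants may still be censored.

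The cost is a few sentences in the SAP, with no extra visit, data cut or follow-up. Because the SAP supersedes the protocol, the SAP edit is enough; Protocol 9.3.1.2 can be aligned at its next amendment.

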5.4.3 Exploratory Efficacy Endpoints

The exploratory efficacy endpoints are listed in Table 1.

5.4.3.1 Biomarker Analysis

Descriptive statistics will be used to evaluate the exploratory biomarkers. Biomarker exploratory analyses will be determined based on study outcomes and further described in a Translational Analysis Plan.

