8.7 BIOMARKERS

The exploratory biomarker objective of this study is to assess tumor tissue and circulating soluble factors, including, but not limited to, deoxyribonucleic acid (DNA), ribonucleic acid

(RNA), enzymes, growth factors, cytokines, antibodies, and immune and tumor cells in tissue and blood, and their association with treatment outcome. Additionally, microbiome profiles may be evaluated from stool samples. Evaluation of baseline levels and/or post-treatment changes from baseline may be performed to determine association with clinical outcomes, including clinical response or lack of response, as well as study intervention tolerability.

- Collection of samples for biomarker research is part of this study. The following samples for biomarker research are required and will be collected from all participants in this study as specified in the SOA ([Table 1](#)) and process in accordance with the laboratory manual:
 - Blood
 - Peripheral blood mononuclear cells (PBMCs)
 - Circulating tumor cells (CTC)
 - DNA
 - RNA
 - Tumor tissue biopsy (archival tumor tissue and fresh biopsies at intervals specified in [Section 4.1](#))
 - Stool
- Samples may be tested for genetic analysis on tumor, stool, and blood samples, including, but not limited to, assays on circulating free DNA, DNA from tumor, stool, blood, and/or immune cells and T cell receptor sequencing may be performed. This research may evaluate whether genetic variations correspond with outcomes of treatment. If genetic variation is found to predict efficacy or AEs, the data might inform optimal use of therapies in cancer patients. Circulating soluble analytes may be assessed that may include but are not limited to immune cytokines, growth factors, antibodies, and/or markers associated with immune characteristics and activation or cancer. Additionally, tumor and blood samples will be collected before and on study intervention for immune and/or tumor cell profiling that may include immune cell phenotyping, enumerations, and/or activation state. Both genome-wide and targeted messenger RNA expression profiling and sequencing in tumor, stool, and/or blood may be performed to define gene signatures that correlate with treatment outcomes. Epigenetic analyses may also be performed as these are important biomarkers for some cancers. Stool samples at baseline and on treatment may be evaluated for microbiome profiling to determine if there is any association with treatment outcome.

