9.3.3.2 Biomarker Analysis

Descriptive statistics will be used to evaluate the exploratory biomarkers. Biomarker exploratory analyses will be determined based on study outcomes and further described in a Biomarker Analysis Plan.

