
• To evaluate tumor and immune biomarkers and their association with treatment outcome (antitumor activity and/or safety).• To estimate the radiographic DOR of each immunotherapy combination in participants with mCRPC.• To evaluate the PK of the components of the immunotherapy combination.• To evaluate the immunogenicity of the components of the immunotherapy combination.	
• Association of tumor and immune biomarkers from tissue, blood, and/or stool with clinical outcomes, including ORR, DCR, rPFS, and tolerability. Biomarkers to be studied will be chosen based on the immunotherapy combination.• Molecular characterization of CTC and evaluation of percent change from baseline.• Enumeration of CTC ≥ 1 at baseline with conversion to CTC0 on treatment.• PSA:
◦ Percent change in PSA from baseline at 12 weeks.◦ Maximum change in PSA at any point after initiation of study intervention.◦ Time to PSA progression, defined as the time from study treatment initiation to the date that a $\geq 25\%$ increase and absolute increase of ≥ 2 ng/mL above the nadir (or baseline value for participants who did not have a decline in PSA) in PSA. The increase must be confirmed by a second consecutive assessment conducted at least 3 weeks later.• DOR: Defined as time from the first tumor assessment that documents radiographic response (CR or PR) to the first documentation of radiographic progression per PCWG3-modified RECIST v1.1 or death due to any cause (whichever occurs first).• Sparse PK analysis.• Presence of ADA against biologic components of each immunotherapy combination.

ADA = anti-drug antibodies; AE = adverse event(s); CR = complete response; CRR = composite response rate; CTC = circulating tumor cells; CTC0 = a measure of zero CTC; DCR = disease control rate; DOR = duration of response; mCRPC = metastatic castration-resistant prostate cancer; ORR = objective response rate; OS = overall survival; PCWG3 = Prostate Cancer Clinical Trials Working Group 3; PK = pharmacokinetics; PR = partial response; PSA = prostate-specific antigen; RECIST = Response Evaluation Criteria in Solid Tumors; rPFS = radiographic progression-free survival; SD = stable disease

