5.7 Interim Analyses

Safety and efficacy will be monitored on a regular basis by the Sponsor and the SAC. Possible adaptations resulting from these data reviews include:

- Modifying or stopping a cohort early based on a safety signal
- Expanding a cohort to include an additional approximately 15 participants (Stage 2) based on acceptable safety data in addition to preliminary signals in clinical activity and/or biomarker results

Other possible adaptations to the study design, including the addition of new combination cohorts, may be based on a variety of factors, such as emerging biological knowledge of mCRPC biomarkers and/or immunotherapy mechanisms, as well as availability of investigational therapies. Findings will not be used to re-estimate the sample size.

Due to the exploratory nature of this study, effect sizes and CIs will not be adjusted to account for ongoing review of data.

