5.7.1 Cohort Expansion Rules

A Simon two-stage minimax design (Simon, 1989) will be implemented for each cohort. In Stage 1, 15 participants will be enrolled. If there are 2 or more responses in these 15 participants, 15 additional participants may be enrolled in Stage 2 for a total of 30 participants in the cohort. For the purposes of cohort expansion, CRR will be used to determine response (ie, CTC response, PSA response, or objective radiographic response).

In addition to efficacy criteria stated above, safety data will also be assessed when determining whether to expand a cohort. If there are ≥ 6 participants meeting cohort-specific toxicity criteria requiring permanent treatment discontinuation, an ad hoc SAC meeting will be held to further review all safety data and provide input on assessing the benefit-risk profile. The SAC will

provide a recommendation in regard to expansion to Stage 2, continuation or discontinuation of the cohort. This ad hoc review will be in addition to the ongoing safety monitoring performed by the SAC, who may recommend terminating a combination cohort at any time for safety reasons. The threshold of 6 participants was chosen because this translates to a posterior probability of 0.69 that the true toxicity rate is > 30%, assuming 15 participants are enrolled per cohort and a minimally informative beta (0.5, 2.5) prior.

If the cohort has an acceptable safety profile but has not demonstrated at least 2 responses, no additional participants will be enrolled into the cohort. However, this decision may be revisited if follow-up translational analysis or emerging external data identifies a subset of participants most likely to derive benefit from the combination therapy that was underrepresented in the cohort. Under this scenario, any modifications to the study design of the combination, including justification for participant selection or enrichment, will be detailed in an amendment to the appropriate cohort appendix.

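### Biomarker analyses may be set after outcomes are known, so a chance association can readily be picked; the decision risk lies in reopening a cohort with 0 or 1 response

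*SAP*

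**What the plan says.** SAP 5.4.3.1 has two sentences. The first sets the method: "Descriptive statistics will be used to evaluate the exploratory biomarkers". The second sets the content: "Biomarker exploratory analyses will be determined based on study outcomes and further described in a Translational Analysis Plan". Protocol 9.3.3.2 carries the same rule under another plan name: "Biomarker exploratory analyses will be determined based on study outcomes and further described in a Biomarker Analysis Plan". Neither document dates or locks that plan.

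Some elements are settled elsewhere. SAP 3.2 says "Biomarkers to be studied will be chosen based on the immunotherapy combination" and gives the exploratory endpoint as "Association of tumor and immune biomarkers from tissue, blood, and/or stool with clinical outcomes, including ORR, DCR, rPFS, and tolerability". Sampling times are in the Schedule of Activities (Protocol 1.3), subject to the cohort appendices. The range of assays is wide. Protocol 8.7 says "Both genome-wide and targeted messenger RNA expression profiling and sequencing in tumor, stool, and/or blood may be performed", and also allows circulating-analyte, T cell receptor and microbiome work, using baseline levels or changes from baseline.

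The results can enter decisions. SAP 5.7 describes expansion as "based on acceptable safety data in addition to preliminary signals in clinical activity and/or biomarker results". SAP 5.7.1 closes a cohort with fewer than 2 responses, then adds that "this decision may be revisited if follow-up translational analysis or emerging external data identifies a subset of participants most likely to derive benefit". Any resulting design change goes into a cohort appendix amendment with a justification. SAP 3.4 allows interim safety and efficacy results to be published before the primary analysis.

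**The concern.** Marker choice by combination can be made in advance. The analysis of those markers is, as worded, made to depend on outcomes. If cut-point, timepoint and pairing are chosen after it is known who responded, an association that separates responders from the rest may be the best of many looks. A reader of the report could not tell, because the SAP does not require pre-listed and data-driven analyses to be distinguished, or the number of looks to be stated.

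Two things are at stake. One is a published biomarker association that is only chance, in a trial whose title names biomarker evaluation as an aim. The other is a decision to reopen or enrich a cohort on the strength of such an association.

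**Working it through.** **Inputs.** From SAP 3.3 and 5.7.1: 15 participants in Stage 1, expansion possible at 2 or more responses, 30 in total, success at 6 or more, response rates of 10% (null) and 25% (alternative). Assumed, because the documents give no value: the number of markers m, the threshold for a notable association, untied continuous markers measured in all participants, and independence between markers. Responder here means the composite response.

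**1. The plan's own figures.** There is none for the biomarker work. The two-stage design reproduces:
- Type I error: sum over x1 = 2 to 15 of Bin(x1; 15, 0.10) × P(X2 ≥ 6 − x1) = 0.0684 (stated 0.07).
- Power: the same sum at 0.25 = 0.7745 (stated 77%).
- Early termination under the null: P(0) + P(1) = 0.206 + 0.343 = 0.549 (stated 55%).

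So 0 or 1 response, the setting for reopening, has probability 55% at a 10% rate and 0.013 + 0.067 = 8% at 25%. Two to four responses have probability 44% and 61%.

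**2. One null marker.** All placements of k responders among n ranks are equally likely. Counting those with AUC ≥ 0.9 or ≤ 0.1:
- 2 of 15: 8/105 = 7.6%
- 3 of 15: 14/455 = 3.1%
- 4 of 15: 24/1365 = 1.8%
- 6 of 30: 776/593775 = 0.13%

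**3. At least one of m independent null markers**, 1 − (1 − p)^m:

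| Responders | m = 5 | m = 10 | m = 20 | m = 50 |
|---|---|---|---|---|
| 2 of 15 | 33% | 55% | 80% | 98% |
| 3 of 15 | 15% | 27% | 46% | 79% |
| 4 of 15 | 9% | 16% | 30% | 59% |

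For 6 of 30 and m = 20: 1 − (1 − 0.0013)^20 = 2.6%, about 3%.

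**4. Sensitivity at m = 20**, for 2, 3 and 4 responders of 15:
- AUC ≥ 0.85 or ≤ 0.15: 91%, 77%, 55%.
- Perfect separation: 32%, 8%, 3%.
- Exact two-sided rank-sum p ≤ 0.05: 54%, 63%, 55%.
- The same p ≤ 0.05 criterion with pairwise correlation 0.5 (simulation, 10,000 runs): 39%, 44%, 40%.

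**5. The reopening case.** With one responder, he is the highest or lowest of 15 on a given null marker with probability 2/15 = 13%. On at least one of m independent markers: 1 − (13/15)^10 = 76% for m = 10, and 1 − (13/15)^20 = 94% for m = 20. With no responders, no responder association can be computed, though rPFS and tolerability remain available.

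**6. SAP 5.7 against 5.7.1.** The and/or in 5.7 can be read as allowing expansion on biomarker results without a clinical signal. In 5.7.1, fewer than 2 responses means no further enrolment unless that decision is revisited. The two sections do not state one rule.

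**The case against.** The strongest reply is that nothing confirmatory is claimed. The biomarker analysis is descriptive and in the exploratory tier, and SAP 5.4 disclaims hypothesis testing and type I error control. Markers are tied to the combination, the main outcomes are listed and sampling times are scheduled, so the freedom is mostly in cut-points, choice among timepoints, and pairing. Reopening needs a justified cohort appendix amendment, and Protocol 10.1.2 requires ethics approval of design changes. The Translational Analysis Plan is not among the documents and may contain more. The phrase about study outcomes could also mean the endpoints rather than the results.

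Most of this stands and limits the point. It does not remove it. An exploratory result can still affect who is enrolled next. The amendment records a justification, but nothing requires it to say whether the marker was pre-listed or how many were examined. If endpoints were meant, the sentence should say so.

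A reader might go further and infer that, with 2 to 4 responders, a chance marker is likely to be reported as a signal and to drive expansion. The documents do not support that:
- Such a cohort already meets the response criterion, so no marker is needed to qualify.
- Whether a chance finding is more likely than not depends on an assumed marker count and threshold; with 20 markers it is 46% and 30% for 3 and 4 responders.
- Reporting it as a signal is inference, since the SAP commits only to description.

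**Conclusion.** The point holds in limited form. As worded, SAP 5.4.3.1 and Protocol 9.3.3.2 allow outcome-driven choice of biomarker analyses, and no lock or labelling rule in either document offsets this. In a Stage 1 cohort a chance association can readily be selected: 30% to 80% for 20 independent null markers at the AUC threshold used, lower under correlation, and about 3% at 6 of 30. These figures rest on an assumed marker count, threshold and independence, and on complete untied data. They show scale and do not predict what this trial will report.

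The consequence differs by setting. With 2 or more responses it is a misleading reported association. With 1 response it is a reopening or enrichment decision resting on one man's rank, where 10 markers give 76%. With none, the responder comparison does not exist.

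**What to change.** Replace the second sentence of SAP 5.4.3.1 with:

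> The Translational Analysis Plan (markers, timepoints, cut-points or continuous use, and the outcome for each association) is finalised before a cohort's biomarker data are linked to its outcome data. Analyses added later are labelled post hoc, and the number of marker-by-outcome associations examined is reported.

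Align Protocol 9.3.3.2, including the name of the plan. In SAP 5.7.1, require any expansion or reopening justification that cites a biomarker to state whether it was pre-listed and how many were examined. Reconcile the and/or wording of SAP 5.7 with the response rule in 5.7.1.

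The cost is earlier sign-off of a plan the SAP already names, and a post hoc label on later ideas, which can still be run. Sample size, endpoints and the two-stage rule are unchanged.
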